Aims/Hypotheses	
Specific Aim 1 - (PRIMARY): Compare the incidence of admission to the NICU in 35⁰-41⁶ week GA non-vigorous newborns receiving Umbilical Cord Milking (UCM) to those receiving Early Cord Clamping (ECC).
 
H1: Compared to ECC subjects, UCM subjects will have a decreased incidence of NICU admission (based on predefined criteria).
 
Specific Aim 2 (SECONDARY): Compare the safety and efficacy profiles in 35⁰-41⁶ week GA non-vigorous newborns receiving UCM to those receiving ECC. Compared to ECC subjects, UCM infants will have:
 
H2: Higher cerebral oxygen saturations in the first 10 minutes of life (sub-study at two (2) sites, n=20).
 
H3: Receive a greater placental transfusion as estimated by hemoglobin levels by 48 hours of life and better blood pressure; will not have increased rates of hyperbilirubinemia compared to ECC subjects; will have decreased resuscitation interventions, level of HIE, use of therapeutic hypothermia, use of volume expanders, and length of hospitalization.
 
H4: Will have improved developmental outcome scores on the Ages & Stages Questionnaire, Third Edition (ASQ-3); UCM subjects will have a lower rate of medium to high risk scores on the MCHAT at 2 years of age.
 
H5: Better cardiac function as measured by echocardiography at 12 hours of life (sub-study at two (2) sites, n=200).

Design and Sample Size	This prospective multi-national cluster randomized crossover (CRXO) trial randomizes by hospital wherein each institution is randomized over time to each arm of the study n=1200 infants – 600 UCM/600 ECC
Inclusion Criteria	
 Non-vigorous newborns born between 35⁰-41⁶ weeks gestation
Exclusion Criteria	
 Known major congenital or chromosomal anomalies of newborn Known cardiac defects other than small ASD, VSD and PDA Complete placental abruption/cutting through the placenta at time of delivery Mono-chorionic multiples Cord anomaly (i.e. avulsion or true knot) Presence of non-reducible nuchal cord Perinatal providers unaware of the protocol Incomplete delivery data Infants born in extremis, for whom additional treatment will not be offered

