We plan to reduce these challenges by using a crossover of clusters. According to this approach, clusters are randomly allocated to receive Treatment A or Treatment B for a suitable period (12 months) and then swap to the other treatment (50). Thus, units randomly allocated to treatment A would then receive treatment B and those initially randomly allocated to treatment B would swap over to treatment A. This cluster randomized crossover control trial (CRXO) design is significantly more powerful than the conventional parallel group cluster RCT, because comparisons are made within the cluster, thereby removing the variation between clusters that can confound conventional cluster trials and leaving only the variation in *changes* in outcome over time between clusters (e.g., how clusters vary in their *changes* in morbidity and mortality rates over time). When there is little such variation, the CRXO design can be remarkably powerful and negate a large proportion of the loss of power due to the clustering in conventional parallel-cluster trials.

Risk

One important premise for CRXO is that the intervention and the control arm are of equal risk. We believe the current evidence supports the concept that UCM is as beneficial as DCC when DCC is not feasible. There is no current evidence for any risk or benefit for UCM or ECC in non-vigorous infants. The pediatric and obstetric co-investigators and administrators at each institution where the study will be conducted support this premise.

Timeline

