Each site has provided the 1-minute Apgar score of 3 or less over the past three years in infants greater than or equal to 35 weeks. The ten sites selected for the trial have an approximate total of 1500 depressed newborns (1-minute Apgar ≤3) at 35-41+6 weeks GA in 2016. Assuming a cluster crossover design will allow 90 percent of infants to be enrolled. Initially it would require about 6 months for training and standardization of all sites. This CRXO study has recruited hospitals that are willing to be randomized for 12 months to one arm of the trial with a cross-over period of up to 2 months for training and education, followed by implementation of the second arm of the trial. Once IRB approval has been obtained, sites will receive randomization by letter from the data center (UCSD ACTRI). They will immediately begin standardizing their cord management to the assigned intervention. As soon as the site PIs have achieved 100 percent compliance over at least 1 month (all non-vigorous infants received assigned intervention) they will let the data center know they are ready to begin the trial. After 50 percent of the subjects are enrolled, all sites will pause enrollment, and immediately begin training and using the alternate cord management (the cross-over period). Enrollment will occur over approximately 26 months (12 months per arm cross over to ensure minimal drift or changes in practice. Based on estimated enrollments, sites will cross over when they have achieved 50 percent of their targeted enrollment or after 1 year of enrollment whichever comes first. We believe using this cluster randomized crossover design with each unit performing the same intervention for infants considered at risk, will result in either intervention (ECC or UCM) being performed with minimal variation for the period of that intervention.

Preparation of sites for the trial

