Each site will be randomized prior to study initiation using a computer-generated scheme prepared by the data center. The lead Biostatistician will inform each site of its randomization status before they begin the trial for education on the intervention. They will also receive another crossover period before beginning the second epoch. Site and investigator standardization will be carried out by the site PIs using a variety of teaching methods and/or video certification process. Each site PI (perinatal provider and neonatologist) will orient their colleagues, delivery room and operating room staff to the study and its protocols. The site PIs will train their providers and staff to ensure that the cord is milked in a consistent method (if in the cord milking epoch), and record time elapsed from delivery until the clamping and cutting of the umbilical cord (both UCM and ECC epoch). This may include review of approved videos, study laminates and protocol. This will also include new staff at sites being trained in the protocol procedures. OB's who have not been trained and are not aware of the protocol, will be excluded from enrolling. Site PI's have agreed to make training new staff a priority to minimize any loss of subjects.

Standardize UCM Procedure

To ensure compliance and adherence of the different sites to the same study intervention(s), the following steps will be taken:

- The detailed process of UCM will be explained and shown in a real time manikin simulated video clip distributed by the Clinical Coordinating Center to the PIs of all participating centers.
- Each sites Neonatal and OB PI will educate their involved staff (OBs, family physicians and midwives) before the launch of the study. This will be accomplished by using the central site video clip, handouts and simulation workshops using manikins.

- The simulation video clip will be available to all sites for download to ensure its availability to the staff all the time.
- Reinforcement of the procedure education will be carried out by the local research team every 1-2 months to ensure compliance of the OB practitioners to the same procedure.

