H5, UCM subjects will have better cardiac function at 12 hours of life (echo Substudy n=200).

Rationale: UCM has demonstrated improved blood pressure, increased pulmonary blood flow cardiac function in preterm infants. However it is unclear whether there are hemodynamic changes in term infants, physiological cardiac measurements on a subset (n=200) of infants of the two sub-study sites (Sharp Mary Birch and Sharp Grossmont Hospital), will be conducted to establish the safety and efficacy of UCM. This aim will further test our hypotheses that infants in the UCM group will have improved early hemodynamics.

Two sites experienced with echocardiography will obtain and report the physiological changes with UCM and ECC at 12 hours of life.

Protocol for Echo Sub-Study

Non-vigorous infants enrolled in the MINVI trial will be approached for consent for ongoing data collection. As part of the data collection, an optional echocardiogram will be performed if the parent consents. The consent will have a check box to indicate if they consent to the additional test.

Echocardiographic measurements will be performed on all infants at 12 hours +/-6 hours of age by our research sonographers who are blinded to infant randomization. Measurements will be taken according to a standard operating procedure to assess systemic blood flow, by superior vena cava (SVC) flow (ml/kg/min), right ventricular output (ml/kg/min), and left ventricular output (LVO) (ml/kg/min). These measurements will be performed off line at a later time. Data will be entered into REDCap.

If any structural abnormalities are found, the attending pediatrician will be notified of the abnormal echocardiogram. The consent will clearly state that this echo is not for diagnostic purposes. Any additional studies including an official complete echocardiogram and or cardiology consultation will be left to the discretion of the attending pediatrician, as he/she deems necessary.

Maintaining Adherence to Algorithms and Minimizing Deviation from Protocol

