Secondary outcomes (use of therapeutic hypothermia, use of volume expanders, hemoglobin, bilirubin, death, and neurodevelopmental follow up scores) will be analyzed using similar multivariable procedures accounting for the study design as for the primary outcome to test treatment effects. Analyses will estimate relative risks and 95% confidence intervals for binary outcomes and means or mean differences and 95% confidence intervals for continuous outcomes. Secondary outcomes will be evaluated for missing data and those with and without missing data will be compared. Multiple imputation analysis will be conducted as warranted. Analyses will also evaluate death as a competing risk. No adjustment for multiple comparisons of secondary outcomes is planned.

Exploratory Analyses

Several outcomes are identified as exploratory (level of HIE, blood pressure, length of hospitalization, resuscitation interventions, and placental pathology). These analyses will focus on descriptive statistics rather than hypothesis testing. Likewise any evaluations of subgroup differences by treatment group (other than race/ethnicity as mentioned previously) will be explored in secondary analyses for descriptive purposes and solely for purposes of generating hypotheses for future studies.

Follow up Study- While all secondary and exploratory outcomes that occur during the delivery hospitalization will be presented in the primary paper, all subjects will continue to be followed until 24 months of age to determine their long-term outcome. The sample size is powered to detect differences in their Ages and Stages Composite and MCHAT scores.

Substudies for cerebral oxygenation and echocardiography will be reported as separate projects on clinical trials.gov and analyzed independently.

VI. Recruitment

Eligibility criteria

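### With two hospitals and four site-epochs, the echo sub-study (H5) cannot carry the confirmatory claim its rationale makes for it

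*Combined protocol and SAP*

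**What the plan says.** The combined protocol and SAP sets H5 in the Protocol Summary (Aims/Hypotheses) as a directional hypothesis under the secondary safety and efficacy aim: "Better cardiac function as measured by echocardiography at 12 hours of life (sub-study at two (2) sites, n=200". In section IV the H5 rationale says that "physiological cardiac measurements on a subset (n=200) of infants of the two sub-study sites" "will be conducted to establish the safety and efficacy of UCM", and that this will test the hypothesis of improved early hemodynamics. The H2 rationale makes the same claim for the NIRS sub-study of 20 infants.

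Allocation is by hospital. Under Trial Design, "clusters are randomly allocated to receive Treatment A or Treatment B for a suitable period (12 months) and then swap to the other treatment". Under Preparation of sites for the trial, "Each site will be randomized prior to study initiation using a computer-generated scheme prepared by the data center". Nothing there pairs or balances the two echo hospitals.

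The Timeline section gives two crossover triggers. One is site-specific: "sites will cross over when they have achieved 50 percent of their targeted enrollment or after 1 year of enrollment whichever comes first". The other is common to all sites: "After 50 percent of the subjects are enrolled, all sites will pause enrollment".

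On analysis, section V says: "Substudies for cerebral oxygenation and echocardiography will be reported as separate projects on clinical trials.gov and analyzed independently". The efficacy endpoint table lists echocardiography as a secondary endpoint marked as a sub-study. It is not on the list of exploratory outcomes in section V. No power, precision, model or limitation is stated for H5.

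**The concern.** In a cluster crossover trial, the relevant error is how much hospitals differ in their change from one epoch to the next. The plan says as much under Trial Design and includes a cluster-by-period term in the primary model. Ten hospitals give some information on that variation. Two do not, and analysing the sub-study separately means that none is planned to be borrowed from the other eight.

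A shift between epochs at one or both hospitals, unrelated to cord management, could therefore be reported as a randomised effect of UCM on cardiac function. The purpose given in the rationale is a property that this sub-study lacks, whatever n is.

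**Working it through.** **Main-trial figure.** There is no echo figure to reproduce, so I first checked the sample-size basis in section V. Inputs: 25% versus 16.25%, two-sided alpha 0.05, 85% power, rho = eta = 0.02, and a correction of 4 x cluster size. Taking cluster size M as infants per site (1200/10 = 120):

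N = 2 x 383 x (1 + 119 x 0.02 - 120 x 0.02) + 4 x 120 = 766 x 0.98 + 480 = 1231

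An unpooled variance gives 1224. Both are within 3% of the stated 1200. The same formula gives 79.0% and 87.1% power for the follow-up scores, against the stated 79% to 87%. So rho = eta, meaning no site-by-period variance, is what the plan assumes for the main trial.

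**The same correction with two hospitals.** With 100 infants per hospital it is 4 x 100 = 400, more than the 200 infants available. Counted per site-epoch it is 4 x 50 = 200, the whole sub-study. The plan does not say that the correction applies to H5. The check shows only that the plan's own allowance for few clusters leaves nothing at two.

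**Four site-epochs.** Let t be the treatment effect, and let pA and pB be the changes from epoch 1 to epoch 2 at hospitals A and B in the absence of any treatment effect.

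*Opposite orders* (A: UCM then ECC; B: ECC then UCM).
- UCM minus ECC at A = t - pA; at B = t + pB.
- Average = t + (pB - pA)/2.
- If pA = pB, the period effect cancels. If not, half the difference stays in the estimate.
- Intercept, site, period and treatment give rank 4 in 4 cells: 0 residual degrees of freedom. Ten sites give 20 cells and rank 12, leaving 8.
- The gap between the two hospitals' own differences is pA + pB, which is what estimates the period effect. It says nothing about pB - pA.

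*Same order* (both UCM then ECC).
- UCM minus ECC = t - pA at A and t - pB at B; average = t - (pA + pB)/2.
- The four-parameter model has rank 3: treatment and epoch are the same variable. One degree of freedom remains for disagreement between hospitals, but t cannot be separated from epoch.

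**Chance of the same order.** The scheme is not stated, so two are assumed.
- Ten sites split 5:5: 2 x C(8,3)/C(10,5) = 2 x 56/252 = 112/252 = 0.444.
- Independent randomisation: 0.50.

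**Illustrative type I error, opposite orders.** Assumptions: 50 infants per site-epoch (200/4), rho = 0.02 carried over to echo outcomes, and a test that uses infant-level error after adjusting for site and period.

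SE ratio = sqrt[(1 + 49 rho - 50 eta)/(1 - rho)]; type I error = 2 x [1 - Phi(1.96/ratio)]

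| eta | numerator | SE ratio | type I error |
|---|---|---|---|
| 0.020 | 0.98 | 1.00 | 5.0% |
| 0.016 | 1.18 | 1.10 | 7.4% |
| 0.010 | 1.48 | 1.23 | 11% |
| 0 | 1.98 | 1.42 | 17% |

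**Illustrative effect of drift, same order.** With 100 infants per arm the standard error is sqrt(2/100) = 0.141 SD. A drift of 0.2 SD between epochs with no treatment effect gives a significant result 29% of the time; 0.3 SD gives 56%.

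**The case against.** Several parts of the opposing case stand.

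- The two orders are not reported. On the assumed schemes, opposite orders have a probability of 50% to 56%, and a common period effect is then removable. A reader might infer that UCM is completely confounded with calendar time; the documents do not establish that. Even with the same order, the site-specific trigger would let the hospitals cross on different dates, making calendar confounding partial. Under the all-sites trigger it would be complete or nearly so. In either case treatment still coincides with study epoch.
- A reader might infer that the 200 infants are presented as individually randomised, or that an infant-level confidence interval is planned. Neither is supported. The trial is described throughout as randomised by hospital, and no echo model is given. Section V says that secondary outcomes will be analysed accounting for the design, although the outcomes it names there do not include echocardiography.
- The sub-study has its own registration and may have its own analysis plan, which was not available here.
- The rho of 0.02 is given for the main-trial outcomes, not for blood-flow measurements, and the lower eta values appear nowhere in the plan.
- Blinded sonographers, a standard operating procedure and off-line measurement limit measurement drift. They do not limit clinical change at a hospital between epochs.
- The claim sits in rationale text, and the primary analysis does not depend on it.

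None of this supplies information on site-by-period change from two hospitals.

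**Conclusion.** The point holds as a limit on what H5 can conclude. With opposite orders, the estimate is valid only if site-by-period change is assumed to be zero, and the sub-study cannot test that. With the same order, the comparison is before-after by epoch. Under neither can two hospitals establish safety or efficacy. The data remain useful as physiology: if rho = eta, 100 infants per arm would detect about 0.40 SD with 80% power (2.80 x 0.141).

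The 7% to 17% range should not be read as the sub-study's actual error rate. It rests on an assumed rho for echo outcomes, assumed eta values and even recruitment; at the plan's own rho = eta = 0.02 the figure is 5.0%. The 44% and 50% rest on assumed allocation schemes.

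Severity: minor. The primary analysis is untouched.

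**What to change.** - In the Protocol Summary and in section IV, label H5 exploratory and physiological, and replace the rationale wording with a descriptive aim. Do the same in the H2 rationale for the NIRS sub-study.
- Report the allocated order at each of the two hospitals and the date each crossed over, since the Timeline section gives two triggers.
- If the orders are opposite, fit site, period and treatment, show each hospital's own UCM minus ECC difference, and state that the confidence interval assumes no site-by-period change.
- If the orders are the same, report a before-after comparison by epoch and do not test H5 as a randomised effect.

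This costs wording in three places and one analysis rule, with no new data, sites or infants. The downside is that H5 becomes a weaker claim.

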Trial Design The planned cluster randomized crossover design has several innovations and benefits over a traditional individual patient randomized controlled trial. Using this design, we will randomize by hospital so that each institution is

randomized over time to each arm of the study. This procedure eliminates institutional and selection bias, minimizes site differences and number of study sites in deriving treatment effect, and improves generalizability as the sample should be more representative of the actual population (22). We chose this design because a traditional RCT would add cost and would take 2-3 times as long to complete enrollment. In the interim, cord management practices may change.

Cluster randomization offers several theoretical advantages over individual randomization (48, 49). The treatments occur in a more realistic delivery room setting—reproducing the way deliveries would function if the intervention was found to be effective and then applied to practice. It allows for recruitment of every patient of interest as an automatic default process that will markedly increase efficiency. It simplifies the consent process, as all patients of interest in that unit will receive the intervention or control during each epoch and parents can 'opt-out' of the system if they wish. It will decrease the cost of the trial because of the decreased burden of antenatal consent and screening. This is possible given that both cord management options are currently performed by providers relatively indiscriminately based on their individual interpretation of related data. The blocks will be standard of care for the year interval at the institution, and there is no more than minimal risk.

In conventional cluster-based trials, the major determinants of statistical power are the number of clusters (in this case the number of labor units) and the variation in outcome within clusters (operationalized by the so called intra-cluster correlation coefficient). Depending on the variations in outcomes at each site, the number of patients in each cluster could have far less impact on statistical power.

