As this is a cluster randomized crossover trial where the standard of care for every non-vigorous infant will be the same over a year at each site it is unlikely there will be a significant portion of newborns that will receive the wrong allocation based on the cluster. The inclusion/exclusion criteria were designed to be minimal and pragmatic for providers to decide readily if the infant should receive the treatment arm. The outcomes for infants with protocol violations will be measured and analyzed according to original allocation by intention-to-treat principles. Only newborns who meet pre-defined exclusion criteria (i.e. cord avulsion or congenital anomaly) will be excluded from the primary analyses, although we will verify that there is not a differential occurrence by treatment from procedure. This strategy was successful in our previous trials.

In prior cord milking trials conducted by [name], protocol violation rates for UCM (milking <4 times) were <5 percent. To ensure optimum compliance, he conducted extensive education and certification of our obstetricians in the delivery room. For the proposed trial, the site investigators all have significant experience with UCM and have equipoise of both cord management techniques. All lead perinatal investigators agreed on the techniques and will ensure their colleagues are adequately trained on the maneuvers to minimize site variability. Sites also agreed on institutional policies to video record the UCM techniques at initial startup to minimize site-to-site and inter-observer variations. Videos will be kept at local sites and used solely for study specific training purposes. Videos will be kept secure per local institutional policies. Site PIs will be considered 'certified' upon agreement of the lead site PI (AK). Training videos and materials will be disseminated to be used as a refresher for delivery room staff, fellows, and attending neonatologists. Monthly teleconference meetings will be conducted to examine site comfort with, and performance of UCM techniques, as well as record keeping, and other study or regulatory issues.

V. STATISTICS

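### The echo sub-study's sonographer blind is not secured, because the arm is the hospital's policy for a whole epoch and nothing conceals that epoch at scanning or off-line reading

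*Combined protocol and SAP*

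**What the plan says.** **The blind.** Under Protocol for Echo Sub-Study (section IV, H5), scans are made "by our research sonographers who are blinded to infant randomization". On timing: "Echocardiographic measurements will be performed on all infants at 12 hours +/-6 hours of age". The outcomes are superior vena cava flow and right and left ventricular output. On reading: "These measurements will be performed off line at a later time". The sub-study runs at Sharp Mary Birch and Sharp Grossmont only, with n=200.

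**The allocation.** Trial Design (section III) explains that "all patients of interest in that unit will receive the intervention or control during each epoch". The section on maintaining adherence adds that "the standard of care for every non-vigorous infant will be the same over a year at each site". Under Timeline, the two arms at a hospital are separated by an enrollment pause, "with a cross-over period of up to 2 months for training and education".

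**The protection that is described.** Prevention of Bias in an unblinded trial (section IV) accepts that obstetrical providers and parents cannot be blinded. It asks that the intervention given be left out of the infant's medical record.

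**The concern.** A claim of blinding to an infant's randomization suits a trial in which each infant is allocated separately. Here there is no infant-level allocation to hide. What has to be hidden is which policy the hospital is running, and the plan describes no step that does so.

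H5 is directional: UCM infants are expected to show better cardiac function. Its outcomes are flow measurements that depend on how the operator obtains and measures the image. Knowledge of the arm could influence either step. If the sub-study were reported as having blinded assessment, readers would credit it with protection that the protocol does not establish.

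**Working it through.** The plan gives no figure for the success of blinding and no power basis for n=200, so there is nothing numerical to reproduce. The check is whether hospital and scan date determine the arm, and whether any described step breaks that link.

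**Step 1: is the arm constant within hospital and epoch?** Yes, by Trial Design and the adherence section. Apart from deviations, every eligible infant in an epoch is managed the same way.

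**Step 2: do the arms overlap in time within a hospital?** No. Timeline has enrollment stop at the crossover while staff train in the other method.

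**Step 3: can the scan date point to the wrong epoch?** The scan window is 12 − 6 = 6 hours to 12 + 6 = 18 hours of age, so the scan falls on the day of birth or the next day. With enrollment paused between epochs, the scan date identifies the epoch.

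**Step 4: what follows?** Given hospital, date and the hospital's current policy, the assigned arm is determined with probability 1. Under individual 1:1 randomization the corresponding figure is 0.5. This describes the design; it does not describe what any sonographer knows.

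**Step 5: do the described measures break the link?**

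| Measure | What it hides | What it leaves open |
|---|---|---|
| Intervention not charted | The entry for that infant | The hospital's policy for the epoch |
| Off-line measurement | Nothing by itself | Date, site and identity on the images; reading order |
| Standard operating procedure for measurement | Not stated | Its content is not reproduced |

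The policy is not confidential within a hospital. Under Preparation of sites for the trial, colleagues and delivery and operating room staff are oriented to the study, with refresher education every 1–2 months. Parents, who also cannot be blinded, consent before the scan.

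**Step 6: must both date and site be masked?** The documents do not give the two hospitals' sequences. If both follow the same order, date alone largely reveals the epoch. If they follow opposite orders, date and site together reveal it. Removing only one is therefore not reliable.

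**Hypothetical illustration only.** Suppose 100 infants per arm, SD = 1, no clustering, and a reading bias of b SD in favour of one arm. None of these except the total of 200 is in the documents. With SE = √(2/100) = 0.141, the false-positive rate of a two-sided 5% test is 1 − Φ(1.96 − b/SE) + Φ(−1.96 − b/SE):

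| b (assumed) | b/SE | False-positive rate |
|---|---|---|
| 0 | 0 | 5.0% |
| 0.1 | 0.71 | 10.9% |
| 0.2 | 1.41 | 29.3% |
| 0.3 | 2.12 | 56.4% |

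This shows that a small bias would matter at this sample size. It is not evidence that one exists, and clustering in two hospitals would change the figures.

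**The case against.** The strongest reply is that hospital and date reveal the arm only to someone who knows the policy in force, and no section says the sonographers know it. The training text names colleagues and delivery and operating room staff, not sonographers. The chart request closes one obvious route. Measurements follow a standard operating procedure that is not reproduced, and the sub-study is registered and analysed separately, so masking may be specified elsewhere.

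Most of this stands. A reader might infer that the sonographers knew every infant's arm, or that the blind has failed. The documents support neither. They show that the arm can be inferred and that no described step prevents it. If the operating procedure already covers masking, a summary and cross-reference in the protocol would settle the matter.

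The reply does not rescue the statement as written. A blind in an epoch-level design needs a mechanism that conceals the epoch, and silence in the chart is not one. Off-line measurement makes such a mechanism possible without supplying it.

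It can also be said fairly that masked reading leaves acquisition exposed, since the choice of window and image affects flow measurements. That is correct, and it is why acquisition should be reported as a limitation.

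**Conclusion.** The concern holds in this form: the plan asserts a blind that its allocation scheme does not secure, and it describes no step that would secure it. What can be inferred is the assigned arm, which is the arm used in an intention-to-treat comparison; treatment received may differ in the few infants with deviations.

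The reach is limited. Section V has the sub-studies reported as separate projects and analysed independently, so the consequence is confined to H5. A reader might extend the point to NICU admission or the main trial's conclusions; the echo readings do not enter those. A reader might also take the illustrative rates as an estimate of bias. They are not: the documents contain no information on whether reading bias occurs, how large it is or in which direction. The conclusion rests on the stated allocation by hospital and epoch, the enrollment pause, the scan window, and the absence of any described masking in the protocol.

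**What to change.** Amend Protocol for Echo Sub-Study as follows.

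1. State that bedside acquisition cannot be assumed blinded, and report this as a limitation.
2. Make the off-line measurement already planned the blinded step. The data center assigns random codes to the stored loops, and date, time, site and patient identifiers are removed from the overlay and the file header.
3. Read the loops in a random order that mixes both epochs and both hospitals, either after both epochs have ended at both sites or in batches that each contain scans from both epochs. Mixed order also prevents drift in reading practice over time from tracking with the arm.
4. If the standard operating procedure already does this, summarize it and refer to it.

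The cost is protocol wording, some de-identification work and later availability of the sub-study measurements. No additional infant, scan or reader is needed. Notification of structural abnormalities to the attending pediatrician continues as the protocol already provides.
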